11.2 The probability and predictive factors for undergoing allogeneic HCT

(1) Based on sample size calculations (see **Sample Size section**), we anticipate total sample of 1000 patients contributing to this analysis. Patients of ≥60 years will be ~500 while those <60 years will be ~500 patients. Among younger patients: we anticipate 40% (n=170) will have high comorbidity scores. The cohort of combined older or medically infirm patients eligible for studying the rate of receiving allogeneic HCT will be approximately 670 patients.

(2) The rate of undergoing allogeneic HCT will be estimated for the whole observed population, comparing older/medically infirm patients to all other patients.

Protocol 2368.00

(3) Data from patients' preferred level of involvement in treatment decision-making will be analyzed by assessing the overall distribution of the most frequent answers among patients who received HCT versus conventional therapy, using chi-squared test. Comparisons of proportion of patients assigning a particular answer as most important will also be done using chi-squared test. The weighted Kappa-statistic will be used to assess the level of agreement or disagreement between the patient's and physician's responses. Marginal Cox model will be used to account for potential correlation between physician and patient preferences.[108]

(4) Differences in QOL scores between baseline and post-treatment assessments for each patient will be tested in an analysis of variance (ANOVA) model.[109]

(5) To identify independent predictive factors for the feasibility of allogeneic HCT, multivariate Cox proportional-hazards regression models will be used, treating HCT as the event of interest and death without HCT as a competing risk. Associations between the potential predictive variables, described under Methods, and the incidence of allogeneic HCT will be evaluated using a backward stepwise approach. Variables that are significantly associated with each outcome event ($P < .05$) will be included as covariate factors in the subsequent comparisons. Time-dependent covariates for multiple post-exposure therapies will be employed using previously described methods.[110] Results will be expressed as HR for each outcome.

11.3 Comparison of outcomes among older and medically infirm AML patients given allogeneic HCT versus conventional therapy

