(1) Older and medically infirm patients who were prospectively enrolled for 2-years under SA2 and who completed initial intensive therapy will then represent a cohort of patients eligible to receive allogeneic HCT or additional conventional therapy ($n=670$). Based on preliminary screen of databases of collaborating centers, we estimate that approximately 25% of the 670 patients will undergo HCT within the time frame of the study. Patients who do or do not undergo HCT will be compared for NRM, OS, DFS, toxicities, QOL, function, utilization and satisfaction with care. Survivors at 3, 6, and 9 months will be compared for these two outcomes.

(2) Primary Outcomes: (i) Proportional hazards regression models for the sub-distributions of competing risks[111] will be used to evaluate impact of HCT and other factors on time-to-event outcomes (NRM, OS, and DFS). Since HCT may be received well after completion of induction and consolidation therapy, it will be analyzed as a time-dependent covariate,[110]so that the comparison is based on patients who have survived for comparable lengths of time. Similarly, patients who are not newly diagnosed at enrollment will be handled via left truncation – i.e., they will enter the set of patients at risk based on time since diagnosis. This analysis will be adjusted for the risk-stratification model, including comorbidities, disease response, age, and other variables; pre-exposure QOL scores; socio-demographic variables, including driving time to treating centers, income, marital status, and other variables; ranks of patient and physician surveys of decision-making style and treatment values; and the institution where the patient was treated. The evaluation of HCT as a risk factor may be complicated by the likely non-proportionality of hazards. In the short-term interval after HCT the risk of death may increase relative to those alive but not transplanted, then decline due to decreased relapse. We will assess this possibility by allowing the hazard ratio for HCT to vary by time after transplant in a time-dependent manner. All P values will be based on likelihood ratio statistics and will be 2-sided. Multivariate P values for a variable will reflect adjustment for all other variables in the model. Measures of precision for the HR or risk differences will be provided in form of confidence intervals.

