(3) Secondary Outcomes: **(i)** The relationship between the choice of treatment (HCT vs. non-HCT) and QOL, function, utilization, and satisfaction scores will be examined. Intra-patient differences will be used to analyze changes in QOL from baseline to follow-up assessments. Basic analyses will utilize paired t-tests (for changes over time) and two-sample t-tests (for comparison between groups). In order to make full use of the longitudinal data we will also use generalized estimating equations (GEEs) approach,[118] which can accommodate the within patient correlation structure and arbitrary patterns of missing data. Further, the GEEs approach would allow for the population-average interpretation which is an advantage over, for example, generalized linear mixed models approach.

(ii) The previously described statistical approaches will be used to adjust the comparisons between recipients of allogeneic HCT and conventional therapy for the pre-exposure measures of QOL and preference scores.

(iii) We will compare the quality-adjusted outcomes using the Q-TWiST methodology which weights survival time according to clinical status (alive without relapse or toxicity, relapse, and toxicity) [119-122]

(4) Tertiary Outcomes: **(i)** The risk factors for mortality after ICU admission in patients with AML will be examined. Survival analysis with logistic regression or Cox proportional hazards model will be used, depending on completeness of patient follow-up. Variables in the model will include the AML-comorbidity model score, history of HCT, AML disease status, absolute neutrophil count, use of life support devices, bacteremia, and creatinine. The above risk factors will be evaluated using AUC and c-statistic to inform development of a potential model to predict ICU mortality. **(ii)** The outcomes of patients with secondary AML will be evaluated as compared to patients with primary AML, after adjusting for percent blasts in the peripheral blood, white blood cell count, and performance status at time of presentation.

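### Section 11.2(5) plans time-dependent covariates for later therapies without naming the therapies or the model; if treatment for relapse enters the 11.3 survival models, the hazard ratio is no longer the total HCT effect

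*Combined protocol and SAP*

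**What the plan says.** Section 11.2(5) describes a multivariate Cox model for receiving HCT, "treating HCT as the event of interest and death without HCT as a competing risk". Three statements close the paragraph:

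- Variables significantly associated with each outcome event "will be included as covariate factors in the subsequent comparisons".
- "Time-dependent covariates for multiple post-exposure therapies will be employed using previously described methods", citing reference 110.
- "Results will be expressed as HR for each outcome".

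Section 11.3(2)(i) then sets out the OS, NRM and DFS models. HCT is the exposure: "it will be analyzed as a time-dependent covariate,[110]so that the comparison is based on patients who have survived for comparable lengths of time". On covariates it says: "This analysis will be adjusted for the risk-stratification model, including comorbidities, disease response, age, and other variables". The list continues with pre-exposure QOL, socio-demographic variables, survey ranks and institution. It names no therapy given after HCT or for relapse. The same paragraph expects the risk of death after HCT to rise at first, "then decline due to decreased relapse".

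Section 11.3(3)(ii) speaks of adjusting comparisons between "recipients of allogeneic HCT and conventional therapy for the pre-exposure measures of QOL and preference scores". Section 8.1.9 collects therapy details at every time-point after enrollment, and any treatment for relapse after transplant, so the data for such a covariate will exist.

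**The concern.** A covariate that is itself changed by the exposure should not enter a model meant to give the exposure's total effect. If HCT prevents relapses, fewer HCT recipients need relapse treatment. A time-dependent indicator for that treatment then absorbs the deaths that HCT avoided by preventing relapse. What remains in the HCT coefficient is mainly the difference in non-relapse mortality, where HCT is at a disadvantage.

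The comparison is a primary objective (5.1.2.1). The plan states no direct-effect estimand and gives no method for covariates affected by earlier treatment. An analyst who followed the sentence into the OS model could report a hazard ratio nearer 1, or above 1, for a treatment that lengthens survival.

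**Working it through.** **1. Which model does the sentence reach?**

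- In the 11.2(5) model HCT is the event. Follow-up for that event ends at HCT, so therapies given after HCT cannot enter it, and it has no HCT effect to distort.
- The preceding sentence points forward to later comparisons, and the following one promises a hazard ratio for each outcome.
- Sections 11.3(2)(i) and 11.3(3)(ii) use *pre-exposure* in adjusting the HCT-versus-conventional comparison. By the same usage, *post-exposure* therapies come after that treatment.

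The outcome models are therefore the most natural target, but not the only possible one (see the objection).

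**2. The plan's own figure.** The plan gives no number for this adjustment. Its one figure for the comparison (Section 11.1) is at least 80% power for a 13-point OS gain, 170 versus 505 patients, two-sided 0.05, ignoring time dependence. Control OS is not stated. At the least favourable value tried, 0.45 versus 0.58:

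- pooled proportion = (505 × 0.45 + 170 × 0.58)/675 = 0.483
- SE under the null = √[0.2497 × (1/505 + 1/170)] = 0.0443
- SE under the alternative = √[0.2475/505 + 0.2436/170] = 0.0439
- power = Φ[(0.13 − 1.96 × 0.0443)/0.0439] = Φ(0.98) = 83.7%

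Over control OS of 10% to 50%, power runs from 83.7% to 97.9%. The statement holds, and this point does not change it.

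**3. The mechanism.** All rates here are assumptions; the documents give none. Patients start in remission and 25% receive HCT at random at time 0. Relapse is 0.6/yr without HCT, death after relapse is 1.5/yr in both groups, death in remission is 0.1/yr without HCT, and follow-up is 18 months. HCT halves relapse and raises death in remission to 0.2/yr. Salvage S(t) starts at relapse and does not alter the death rate. The adjusted model is h(t) = h₀(t) exp[β·HCT + γ·S(t)].

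If every relapsed patient is salvaged, S(t) is simply a relapse indicator:

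- while S = 0, the HCT hazard ratio is 0.2/0.1 = 2
- while S = 1, it is 1.5/1.5 = 1

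The adjusted hazard ratio must fall between 1 and 2, however many relapses HCT prevents. With equal non-relapse mortality both strata give 1, so a true benefit disappears. If only some relapsed patients are salvaged, the rest stay in S = 0 and part of the relapse benefit remains in β.

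**4. Size.** OS hazard ratio for HCT, without → with the salvage covariate (300,000 simulated patients, piecewise-exponential fit):

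| Relapsed patients salvaged | Relapse HR 0.5, NRM 0.1 to 0.2 | Relapse HR 0.35, NRM 0.1 to 0.2 | Relapse HR 0.5, NRM equal |
|---|---|---|---|
| 100% | 0.88 → 1.30 | 0.76 → 1.36 | 0.65 → 1.02 |
| 70% | 0.87 → 1.11 | 0.76 → 1.08 | 0.64 → 0.84 |
| 50% | 0.88 → 1.04 | 0.77 → 0.96 | 0.64 → 0.76 |
| 30% | 0.88 → 0.96 | 0.76 → 0.87 | 0.64 → 0.71 |

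A separate run gave 0.88 → 1.31 (NRM doubled) and 0.63 → 0.97 (NRM equal) with all salvaged, and 0.90 → 0.98 and 0.65 → 0.72 with 30%. Salvage does not affect death here, so the unadjusted values within a column differ only by simulation error.

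**5. Other assumed rates.** Two years' follow-up, relapse 0.7/yr, relapse HR 0.4, NRM 0.15 versus 0.05, death after relapse 1.5/yr:

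- all salvaged, no effect on death: 0.70 → 1.30
- 70% salvaged, death hazard × 0.8: 0.72 → 1.01
- 30% salvaged, death hazard × 0.8: 0.71 → 0.79
- 30% salvaged, death hazard × 0.3: 0.77 → 0.77

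If HCT has no effect at all, the ratio stays at 1.00.

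**6. A repair that fails.** One might update therapy history until HCT and freeze it there. Untransplanted patients would then still be adjusted for relapse therapy while HCT recipients would not. At the step 3 rates the hazard ratio went from 0.88 to 3.44 with all salvaged and from 0.87 to 1.65 with 70%, further from the total effect than the symmetric covariate.

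**The case against.** The strongest reply is that the plan never says relapse therapy enters the outcome models.

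- The sentence stands under the HCT-incidence model. If *exposure* there means initial therapy, later consolidation or salvage before transplant is a legitimate time-dependent predictor of HCT. Section 4.0 says outcome comparisons are adjusted for QOL collected at baseline, which fits that meaning.
- Reference 110 is cited again in 11.3(2)(i) for HCT as a time-dependent covariate. The sentence may announce only that device, which guards against immortal-time bias.
- The promise of a hazard ratio for each outcome could refer to the two events of 11.2(5), HCT and death without HCT.
- The 11.3 adjustment list is detailed and names no such therapy. Nor do the landmark, weighted, doubly robust or matched analyses.
- Universal salvage is a worst case. Section 8.0 counts follow-up and supportive care among the non-HCT options.

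Much of this stands. A reader might infer that the plan commits to adjusting for relapse treatment and will therefore remove or reverse the HCT effect. The documents do not support that: the commitment is one reading of an unspecific sentence, and reversal needs particular rates.

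The reply does not settle the matter, however. The sentence speaks of several therapies after the exposure, which describes HCT itself poorly, and 11.3(2)(i) already specifies time-dependent HCT. The open-ended mention of other variables excludes nothing. Reference 110 is listed as a report of long-term outcome in children with relapsed ALL, and its title does not settle the meaning.

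**Conclusion.** The sentence is under-specified, and its most natural reading puts post-treatment therapies into the 11.3 outcome models. If treatment for relapse is among them, the OS hazard ratio is not the total HCT effect. That follows from the plan's own account of how HCT lowers late mortality and needs no simulation.

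The size does rest on assumption: constant rates, HCT at random at time 0 and salvage starting at relapse. Attenuation is the usual result. Removal or reversal appears when most relapsed patients are salvaged (0.88 to 1.31 with all). With 30% salvaged the shift is small (0.90 to 0.98) or absent (0.77 to 0.77). Every figure concerns OS; the NRM model was not computed. DFS is little affected, because relapse is ordinarily itself a DFS event.

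This should be corrected before analysis. Confidence that the sentence was meant for the outcome models is moderate.

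**What to change.** 1. In 11.2(5), limit the sentence to the HCT-incidence model: therapies given before HCT, as time-dependent predictors of HCT.
2. In 11.3(2)(i), state that the OS and NRM models contain HCT as the time-dependent exposure plus pre-exposure covariates. Therapies started after HCT, or for relapse in either group, are reported descriptively and not entered as covariates.
3. Do not use a rule that updates therapy until HCT and then freezes it.
4. If salvage before HCT is to be handled as a time-varying confounder, put it in the model for receiving HCT that builds the inverse-probability weights (11.3(2)(iii)), not in the outcome regression.
5. If a direct effect is wanted, name it as the estimand and use a suited method, such as a marginal structural model.

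Items 1 to 3 cost SAP wording only. Items 4 and 5 are optional and add analysis work. None changes sample size, data collection or patient care.

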4.0 PROPOSAL

We will investigate in a prospective, longitudinal, observational, multi-institutional study the frequency of receiving allogeneic HCT among patients with AML or MDS considered for induction therapy at multiple institutions. Our primary goal here is to investigate how often older and medically infirm AML patients are referred to undergo allogeneic HCT. We will collect data on outcome-discriminative criteria, such as age, intensity of induction treatment, performance status, cytogenetic risks, and high white blood; in addition to data on patients and physician attitudes towards decision-making style and choice of therapy, socio-demographic variables, and baseline QOL to assess reasons patients may not be offered allogeneic HCT. We will evaluate differences between patients who receive versus those who do not receive allogeneic HCT by comparing the previously mentioned characteristics.

We would like also to understand who benefits from allogeneic HCT and to provide better tools for identifying these patients. Conversely, it is also important to identify patients for whom allogeneic HCT is not recommended because of relatively high treatment-related morbidity and mortality. Other important considerations in these judgments are the toxicity of treatment and the QOL experienced by survivors of either treatment approach. We will observe the two groups of patients who will be treated with allogeneic HCT or conventional therapy over 24 months. Outcome comparisons will be carefully adjusted for differences between patients in comorbidities and outcome-discriminative criteria, socio-demographic factors, decision-making preferences, and baseline QOL scores, which were collected at baseline assessment. These data will help individualize future treatment recommendations.

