5.0 OBJECTIVES

5.1 Primary objectives

- 5.1.1 Feasibility of allogeneic HCT in older and medically infirm patients with AML
 - 5.1.1.1 Estimating the probability of undergoing allogeneic HCT among older and medically infirm AML patients compared to younger and relatively healthier patients.
 - 5.1.1.2 Comparing the characteristics of patients who did versus did not proceed to allogeneic HCT.
- 5.1.2 Comparison of outcomes among prospectively enrolled older and medically infirm AML patients given allogeneic HCT versus induction therapy
 - 5.1.2.1 Non-relapse mortality (NRM), overall (OS), and disease-free survival (DFS).
 - 5.1.2.2 QOL

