11.0 STATISTICAL CONSIDERATIONS

11.1 Introduction and sample size

To improve the strength of the findings as well as reporting of these findings, we will follow the recommendations of STROBE Statement (see study document ‘STROBE Criteria’) which provides guidelines of how to discuss and report study design, analysis, and findings in manuscript writing.

There is no targeted number for enrollment on this study. Instead, we plan to enroll all eligible patients continuously for duration of 36-40 months from study activation. We anticipate enrolling approximately 1000 patients from all sites but we will allow enrollment of more patients if enrollment rates were unexpectedly higher.

Based on a preliminary screen of the SCCA records over years 2008-2009, approximately 180, 125, 120, and 75 eligible patients with AML were seen annually at the 4 collaborating institutions, respectively, for an annual total of 500 patients. We anticipate enrollment rate of approximately ~65% resulting in a total of approximately 1000 patients observed over 3 years. Based on a preliminary screen, we anticipate that 50% (n=500) will be ≥60 years of age. Among the remaining 500 younger patients, we would anticipate (based on historical distribution of comorbidity scores among HCT recipients) that approximately 35% (n = 170) will have significant comorbidities (scores of ≥3). This suggests that the combined cohort of older or medically infirm patients eligible for studying the rate of receiving allogeneic HCT will be approximately 670 patients over 3 years. **Table 2** shows an estimate of the minimal increment in incidence of HCT detectable with 80% power at the 2-sided 0.05 level of significance, for varying assumptions about the prevalence of the risk factor. These estimates assume a time-to-event analysis, 25% overall incidence at 2 years post-initial therapy and 25% incidence of death without HCT as a competing risk.

Prevalence of risk factor or group	Increment in HCT incidence (HR)
10%	0.17 (1.9)
20%	0.13 (1.7)
30%	0.11 (1.6)
40%	0.10 (1.6)

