For the comparison study, power calculations are complicated by the time-dependent nature of the treatment groups, as well as by likely non-proportionality in the hazard ratio for HCT. Were these factors not present, the expected 170 patients undergoing HCT compared to 505 who do not undergo HCT, would provide at least 80% power to detect an increase in OS of 13%, at the 2-sided 0.05 level of significance. Because of the large number of unknown assumptions it is nearly impossible to estimate the true power for the actual analysis that will be done, other than that the detectable effect size is likely considerably larger than 13%. Nevertheless, based on previous experience with time-dependent analyses (such as of chronic graft-versus-host disease after HCT),[107] the overall sample size should be sufficient to detect effects of meaningful clinical magnitude.

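### Section 11.3(1) gives n=670 to patients who finished intensive therapy, but 11.1 and 11.2 derive 670 as all older or infirm enrollees

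*Combined protocol and SAP*

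**What the plan says.** Section 11.1 builds the cohort from enrolment: "We anticipate enrollment rate of approximately ~65% resulting in a total of approximately 1000 patients observed over 3 years". Half of these (500) are expected to be aged 60 or over. Of the 500 younger patients, "approximately 35% (n = 170) will have significant comorbidities (scores of ≥3"). The combined cohort "eligible for studying the rate of receiving allogeneic HCT will be approximately 670 patients over 3 years".

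The power statement for the outcome comparison, also in 11.1, reads "the expected 170 patients undergoing HCT compared to 505 who do not undergo HCT, would provide at least 80% power" for a 13-point increase in OS at the two-sided 0.05 level.

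Section 11.2(1) repeats 670 out of a total of 1000, but gives the younger infirm share as 40% with the same n of 170.

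Section 11.3(1) then says that older and infirm patients, enrolled for two years, who "completed initial intensive therapy will then represent a cohort of patients eligible to receive allogeneic HCT or additional conventional therapy ($n=670"), and expects about 25% of the 670 to be transplanted.

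Two other places bear on whether those groups can be the same size. Section 6.1.1.1 admits patients starting low-dose single-agent or hypomethylating therapy as well as intensive induction. Section 3.1 cites day-30 non-relapse mortality of up to 25% in older AML patients.

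**The concern.** One number is attached to two populations. In 11.1 and 11.2 it is everyone enrolled who is older or infirm. In 11.3(1) it is the part of that group that received and finished intensive therapy. They coincide only if every older or infirm enrollee does so, and the eligibility criteria and the cited early mortality rule that out as a planning assumption.

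The comparison is a primary objective (5.1.2). An analyst who applies 11.3(1) as written would leave out less-intensively treated patients and those who die before finishing. The n, the expected transplant count and the 170/505 power basis would then describe a larger group than the one analysed. An analyst who works from the n would keep those patients. Neither term in the condition is settled: criteria for intensive treatment are still to be developed under 5.3.1, and completion is not defined.

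The condition also affects the time axis. Section 11.3(2)(i) specifies delayed entry only for patients not newly diagnosed at enrolment. If membership depends on completion while follow-up starts earlier, every member has guaranteed survival up to completion.

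**Working it through.** **Reproducing 670.** Inputs from 11.1:
- Enrolment: 500 per year × 3 years × 0.65 = 975, stated as about 1000.
- Aged 60 or over: 0.50 × 1000 = 500.
- Younger with scores of 3 or more: 0.35 × 500 = 175, stated as 170.
- Combined: 500 + 170 = 670 (675 with the exact 35%).

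There is no term for therapy type, early death or completion. The figure reproduces only as the full enrolled cohort.

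**The 170/505 split.** 170 + 505 = 675, and 170/675 = 25.2%. It can come from 675 (0.25 × 675 = 168.75, leaving about 505) or from 670 (167.5 and 502.5, rounded up). Both start from the full count.

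**The power statement.** I used a normal approximation for two proportions, with pooled variance under the null and unpooled under the alternative. With baseline OS assumed at 35%, p1 = 0.48, p2 = 0.35, n1 = 170 and k = 505/170 = 2.97:
- Pooled p = (0.48 + 2.97 × 0.35)/3.97 = 0.383.
- Null term: 1.96 × √(0.383 × 0.617 × (1 + 1/2.97)) = 1.101.
- Alternative SD: √(0.48 × 0.52 + 0.35 × 0.65/2.97) = 0.571.
- z = (0.13 × √170 − 1.101)/0.571 = 1.04, so power is 85%.

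Over assumed baselines of 10% to 50%, power for 13 points is 84% to 98%. The claim of at least 80% therefore holds for the full cohort, under the simplifications 11.1 itself names.

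**If the completion condition is kept.** n = 670 × f, where f is the share completing intensive therapy. The documents give no f. The values below are assumptions, at baseline OS 35%, for scale only.

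| f | n | Detectable at 80% power, 25% transplanted | Power for 13 points, 25% transplanted | Detectable if all 170 recipients are completers |
|---|---|---|---|---|
| 1.0 | 670 | 12.2 points | 85% | 12.1 points |
| 0.9 | 603 | 12.9 | 81% | 12.4 |
| 0.8 | 536 | 13.7 | 76% | 12.7 |
| 0.6 | 402 | 15.8 | 64% | 13.9 |
| 0.5 | 335 | 17.3 | 56% | 15.1 |

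In the last column the transplant share rises from 25% to 170/603 = 28% at f = 0.9 and 170/335 = 51% at f = 0.5, so the 25% would need restating too.

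**The 40% in 11.2.** 0.40 × 500 = 200, not 170, and 500 + 200 = 700, not 670. The 35% in 11.1 gives 175, which rounding can reconcile with 170.

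**The case against.** The strongest reply is that the condition is deliberate and only the n was carried over. Section 11.3(1) describes a sequence in which patients finish initial therapy and then become eligible for transplant or further conventional treatment, and 11.3(2)(ii) counts its landmarks from induction. This stands. It means the clause cannot simply be presumed the mistake, but it does not rescue the n.

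A reader might infer that the clause must be the error because 4.0 lists "outcome-discriminative criteria, such as age, intensity of induction treatment, performance status, cytogenetic risks" and says "Outcome comparisons will be carefully adjusted for differences between patients in comorbidities and outcome-discriminative criteria". That does not follow. The expert survey in section 7.0 grades intensive regimens as high or intermediate, so intensity varies within an intensive-only cohort. Objective 5.1.2, "Comparison of outcomes among prospectively enrolled older and medically infirm AML patients given allogeneic HCT versus induction therapy", has no completion condition, but objectives often leave out analysis-set conditions. Its comparator label also differs from the conventional therapy of 11.3, so its wording is weak evidence of the intended cohort.

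A second reply is that 670 is approximate and controls nothing: 11.1 sets no enrolment target and warns that the true detectable effect is probably well above 13 points. This limits the consequence. But rounding explains 670 against 675, not a subset as large as the whole, and the warning concerns time-dependence and non-proportional hazards, not who is analysed.

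A reader might also take the two-year phrase in 11.3(1) as contradicting the three-year accrual in 11.1. Sections 2.0 and 4.0 describe 24 months of follow-up, which the phrase may mean, so no error is established.

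**Conclusion.** The mismatch is real and should be corrected before analysis. The figure of 670 and the 170/505 power basis belong to all enrolled older or infirm patients, while 11.3(1) assigns 670 to a group that must be smaller under the protocol's own eligibility and background figures. This conclusion rests on the text and simple sums, not on a power formula.

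The size of the shortfall cannot be computed: no completion share is given, and the denominator behind the 25% transplant share is not described. The table shows scale under assumed shares only. A reader might infer from it that the comparison is underpowered; the documents do not support that, because the loss depends on an unknown share and on which population is meant, and 11.1 already declines to estimate the true power.

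The documents also do not settle whether the clause or the n is wrong. The 40% in 11.2 is a plain arithmetic slip. The two-year phrase is unclear, not shown to be wrong.

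**What to change.** State the 11.3 population once and match the n to it, in one of two ways.

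(a) Remove the completion condition. The cohort is then all enrolled patients who are 60 or over or have a comorbidity score of 3 or more, with n about 670 and the 170/505 split unchanged.

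(b) Keep the condition. Define intensive and completed before analysis, start follow-up for this comparison at completion, and restate n, the expected transplant count, the 170/505 split and the 13-point detectable difference for the smaller cohort. This needs a stated completion share with its source.

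Under either option, correct the 40% in 11.2 to agree with the 35% in 11.1, and say whether the two years in 11.3(1) are follow-up or accrual. If accrual is meant, reconcile the n with the three years in 11.1.

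Option (a) costs wording only. Option (b) adds definitions and a recalculation that may look less favourable. Neither requires more patients.
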